5.2.4 Cycle 1: Days 2–4

Tumor lysis labs will be drawn daily for the first three days (72 hours) following the first alvocidib dose (ie, Days 2–4).

5.2.5 Cycle 1: Day 22 (±3 days)

In the event that there is a delay in starting the next cycle, the below procedures should be done weekly (approximately every 7 days, or more frequently if clinically indicated) and recorded as unscheduled visit:

- Abbreviated physical examination (AE- or symptom-directed exam)
- Assess ECOG PS ([Appendix B](#))
- Vital signs (temperature, heart rate, systolic and diastolic blood pressures, and respiratory rate)
- Record only those medications (prescription, nonprescription, nutritional supplements) administered in conjunction with an AE
- Collect blood for evaluation of laboratory parameters ([Appendix D](#)):
 - Hematology
 - Tumor lysis labs to be drawn at least weekly for the remainder of Cycle 1
 - Fibrinogen level (as clinically indicated)
- Assess for AEs
- Review study diary and remind patient to bring diary back at next clinic visit

5.2.6 Cycle 1: Day 28 (±3 days)

- Collect bone marrow and peripheral blood for response assessment and PD tests ([Section 7.3](#)). Collect bone marrow sample to be sent to a central laboratory for MRD assessment using standardized techniques (ie, MPFC and molecular testing including NGS) ([Appendix D](#)). If the

procedure is nonproductive or not diagnostic, it must be repeated within 7-10 days. In addition, 6 to 8 bone marrow slides will be prepared and sent to the Sponsor. Details regarding the collection and shipping of these slides is provided in the Laboratory Manual.

- Record only those medications (prescription, nonprescription, nutritional supplements) administered in conjunction with an AE
- Assess for AEs
- Review study diary and remind patient to bring diary back at next clinic visit

5.3 Cycles 2+

Patients who achieve CR, CRi, CRh, MLFS, PR, or clinical benefit after the first cycle (completion of all doses) may receive additional optional cycles of treatment until disease progression (in the event of toxicities see the recommendations in [Table 3](#), if applicable).

Those who achieve a CR, CRi, CRh, or MLFS (ie, <5% blasts in bone marrow) should not be given **subsequent cycles** until ANC >0.5 and platelets >50. If treatment is delayed >2 weeks for cytopenias, a bone marrow biopsy should be performed to reassess disease status.

Patients not demonstrating evidence of CR, CRi, CRh, MLFS, PR, or clinical benefit after 4 cycles of treatment will be considered for removal from the study, although with permission of the Medical Monitor, treatment may continue if clinically indicated (in the event of toxicities see the recommendations in [Table 3](#), if applicable).

There is a maximum limit of 6 weeks between the start of cycles unless otherwise discussed with the medical monitor.

5.3.1 Cycles 2+: At Least 2 Hours Prior to First Dose (± 3 days)

During Cycles 2+, pretreatment IV hydration, oral allopurinol, and oral phosphate binder may be discontinued if serum uric acid and phosphorus levels are within normal limits and there is no evidence of TLS.

Should TLS be suspected during subsequent cycles, perform the following procedures at least 2 hours prior to starting therapy on Day 1 (unless otherwise stated):

- Initiate supportive care measures prior to first dose in all patients to minimize the likelihood of TLS:
 - Administer pretreatment IV hydration and determine if oral allopurinol and oral phosphate binder are still clinically indicated (see [Section 4.5.1](#))

- Assess patient for adequate hydration at all study visits and replace excessive fluid losses, including from diarrhea, unless otherwise clinically indicated ([Section 4.5.1.2](#) and [Section 4.5.1.3](#))
- Review study diary and remind patient to bring diary back at next clinic visit

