	
Supportive Care (Stage 1 and Stage 2)
 
Supportive care will be provided including:
 
• Tumor Lysis Prevention and Treatment
○ Due to an increased likelihood of TLS, hospitalization of patients with monocytic differentiation and/or a peripheral blast count of >10,000/mm³ is strongly recommended for the first dose of alvocidib (ie, Cycle 1 / Day 1).○ Mandatory IV hydration with 0.45% NaCl (or similar hydration fluid per institutional standard) sterile solution at 250-500 cc for 1-2 hours prior to alvocidib, then an additional 250-500 cc for 1-2 hours after alvocidib during Cycle 1 (optional for subsequent cycles for patients who have achieved a CR).• Replacement of excessive fluid losses, including from diarrhea, should be done unless otherwise clinically indicated.
○ Alvocidib is known to induce mild diarrhea during treatment days. Over-the-counter measures are typically effective in this setting if initiated early. Persistent diarrhea despite optimal outpatient management would trigger medical consultation. Early consideration should be given for possible Clostridioides difficile infection in this patient population and identifying/treating as expeditiously as possible should be top of mind.• Mandatory oral allopurinol to be started at least 72 hours prior to Day 1 of Cycle 1 and continued until completion of the first cycle (ie, 28 days). This may be discontinued for subsequent treatment cycles if uric acid levels are within normal limits and there is no evidence of tumor lysis syndrome.• Mandatory oral phosphate binder to be started at the same time as initiation of IV hydration on Day 1 of Cycle 1 and continued for the first week (ie, 7 days).
○ If serum phosphorus levels are <3 after the first treatment with alvocidib and there is no evidence of TLS, phosphate binders may be discontinued. Patients should continue to

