4.5.1.1 Hyperkalemia and Tumor Lysis Syndrome

Tumor lysis may occur as part of initial cytoreductive therapy. The most extreme form, known as Tumor Lysis Syndrome (TLS), is characterized by hyperkalemia, hyperuricemia, hyperphosphatemia, increased lactate dehydrogenase (LDH), coagulopathy, and a potential cytokine release

syndrome. ***Due to an increased likelihood of TLS, hospitalization of patients with monocytic differentiation and/or a peripheral blast count of >10,000/mm³ is strongly recommended for the first dose of alvocidib (ie, Cycle 1 / Day 1).***

- Mandatory IV hydration with 0.45% NaCl (or similar hydration fluid per institutional standard) sterile solution at **250-500 cc** for 1-2 hours prior to alvocidib, then an additional **250-500 cc** for 1-2 hours after alvocidib during Cycle 1 (optional for subsequent cycles for patients who have achieved a CR).
- Replacement of excessive fluid losses, including from diarrhea, should be done unless otherwise clinically indicated.
 - Alvocidib is known to induce mild diarrhea during treatment days. Over-the-counter measures are typically effective in this setting if initiated early. Persistent diarrhea despite optimal outpatient management would trigger medical consultation. Early consideration should be given for possible *Clostridioides difficile* (*C. difficile*) infection in this patient population and identifying/treating as expeditiously as possible should be top of mind (see [Section 4.5.1.2](#)).
- Mandatory oral allopurinol to be started at least 72 hours prior to Day 1 of Cycle 1 and continued until completion of the first cycle (ie, 28 days). This may be discontinued for subsequent treatment cycles if uric acid levels are within normal limits and there is no evidence of TLS.
- Mandatory oral phosphate binder to be started at the same time as initiation of IV hydration on Day 1 of Cycle 1 and continued for the first week (ie, 7 days).
 - If serum phosphorus levels are <3 after the first treatment with alvocidib and there is no evidence of TLS, phosphate binders may be discontinued. Patients should continue to be monitored for TLS as outlined for subsequent treatment cycles. Caution is warranted for patients who still have a high blast count as they remain at risk for TLS with subsequent treatments.
- Evaluation of laboratory indicators of TLS during initial therapy (may be adjusted for subsequent cycles based on extent of tumor burden):

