a Dose is only adjusted at the beginning of each cycle after Cycle 1 if there has been a > 10% change in weight compared to the weight used to calculate the current dose.

b Required at C1 and then every even cycle thereafter (i.e. C2, C4, etc).

c Bone marrow and peripheral blood are not collected if collected in the previous 30 days

d Year 1: Phone calls monthly (±5 days) beginning the month after the patient completes the end-of-study assessments to 12 months after End of Treatment visit regardless of how many cycles a patient receives (Year 1=Day of First Treatment plus 12 months).
Year 2: Phone calls every other month (±5 days) during Year 2 (Months 14 to 24 after End of Treatment visit).

* as clinically indicated

** only required if last pregnancy test was >72 hrs from C1D1 visit

*** optional for subsequent cycles for patients who have achieved a CR

Arm 2 (ALV): Schedule of Activities

TESTS/PROCEDURES	SCREENING										ALL TREATMENT CYCLES (CYCLE = 28 DAYS)					
	-14 days	-72 hours	D1	D2	D3	D4	D8	D15	D22	D28	EOT	FU				
Visit window																±5d
Obtain ICF	X															
Medical history	X															
Full PE	X	X C2+														
Abbreviated PE		X C1														
BSA		X														
Weight (kg)	X	X ^a														
Height (cm)	X	X														
ECOG	X	X														
Vital signs	X	X														
Bone marrow & peripheral blood	X															
Cytogenetic profiling	X															
12-lead ECG	X															X*
Pregnancy test	X	X (**C1)														
Hematology	X	X C2														
Full chemistry panel	X	X C2+														
Pre-infusion TLS labs		X Only C1														
Post-infusion TLS labs		X Only C1	X Only C1	X Only C1	X Only C1	X Only C1	X Only C1	X Only C1	X Only C1	X Only C1	X					
Coagulation		X C2+*														
Urinalysis		X														X
Blood transfusions			Recorded from 56 days prior to first study treatment dose, through 56 days after last dose of study treatment													
Lumbar puncture for CNS disease		X*														
Review Inc/Exc Criteria		X														
Daily oral allopurinol			Mandatory from 72 hours prior to D1 up to C1/D28. As clinically indicated for subsequent cycles.													
IV hydration pre & post infusion			X C2+***										X C2+***	X C2+***		
Oral phosphate binder													For C1, mandatory			
Assess patient's hydration level																
Prophylactic antibiotics, antifungals per site SOC																

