• Complete remission (CR)	Bone marrow blasts <5%; absence of circulating blasts and blasts with Auer rods; absence of extramedullary disease; absolute neutrophil count $\geq 1.0 \times 10^9/L$ (1,000/ μ L); platelet count $\geq 100 \times 10^9/L$ (100,000/ μ L)	MRD positive or unknown*
• CR with incomplete hematologic recovery (CR _i)	All CR criteria except for residual neutropenia [$<1.0 \times 10^9/L$ (1,000/ μ L)] or thrombocytopenia [$<100 \times 10^9/L$ (100,000/ μ L)]	
• Morphologic leukemia-free state (MLFS)	Bone marrow blasts <5%; absence of blasts with Auer rods; absence of extramedullary disease; no hematologic recovery required	Marrow should not merely be “aplastic”; at least 200 cells should be enumerated or cellularity should be at least 10%
• Partial remission (PR)	All hematologic criteria of CR; decrease of bone marrow blast percentage to 5% to 25%; and decrease of pretreatment bone marrow blast percentage by at least 50%	Especially important in the context of phase 1-2 clinical trials

*Including patients with morphologic CR who are MRD+ and cytogenetic and/or molecular marker positive.

2017 EUROPEAN LEUKEMIANET RECOMMENDATIONS (Cont)

Category	Definition	Comment
Treatment failure		
• Primary refractory disease	No CR or CR _i after 2 courses of intensive induction treatment; excluding patients with death in aplasia or death due to indeterminate cause	Regimens containing higher doses of cytarabine (see Table 8) are generally considered as the best option for patients not responding to a first cycle of 7+3; the likelihood of responding to such regimens is lower after failure of a first
• Death in aplasia	Deaths occurring ≥ 7 days following completion of initial treatment while cytopenic; with an aplastic or hypoplastic bone marrow obtained within 7 days of death, without evidence of persistent leukemia	
• Death from indeterminate cause	Deaths occurring before completion of therapy, or <7 days following its completion; or deaths occurring ≥ 7 days following completion of initial therapy with no blasts in the blood, but no bone marrow examination available	

2017 EUROPEAN LEUKEMIANET RECOMMENDATIONS (Cont)

Category	Definition	Comment
Response criteria for clinical trials only		
• Stable disease	Absence of CR _{MRD} , CR, CR _i , PR, MLFS; and criteria for PD not met	Period of stable disease should last at least 3 months

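### Protocol Section 5.3.1 lets pretreatment IV hydration stop from Cycle 2 on normal labs, while the synopsis, Section 4.5.1.1 and Appendix A make it optional for patients in CR

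*Protocol*

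**What the plan says.** **Section 5.3.1 (Cycles 2+).** One sentence covers three measures: "pretreatment IV hydration, oral allopurinol, and oral phosphate binder may be discontinued if serum uric acid and phosphorus levels are within normal limits". It adds that there must be no evidence of TLS. The next sentence reads "Should TLS be suspected during subsequent cycles, perform the following procedures at least 2 hours prior to starting therapy on Day 1", and the first procedure listed under it includes pretreatment IV hydration. The section does not mention post-infusion fluid.

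**Section 4.5.1.1.** Each measure has its own stopping rule:
- IV hydration before and after alvocidib is mandatory "during Cycle 1 (optional for subsequent cycles for patients who have achieved a CR").
- For allopurinol: "This may be discontinued for subsequent treatment cycles if uric acid levels are within normal limits and there is no evidence of TLS".
- The phosphate binder may stop if phosphorus is below 3 after the first alvocidib treatment and there is no evidence of TLS. A warning follows: "Caution is warranted for patients who still have a high blast count as they remain at risk for TLS with subsequent treatments".

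**Synopsis, Supportive Care.** The hydration rule is the same as in Section 4.5.1.1.

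**Appendix A (repeated in SAP Section 18).** The row for hydration before and after infusion is marked for Cycles 2+, with a footnote: "optional for subsequent cycles for patients who have achieved a CR".

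**The concern.** Section 5.3.1 puts hydration under a lab rule that resembles the allopurinol and binder rules of Section 4.5.1.1, and the CR condition on hydration is lost. A site following Section 5.3.1 may drop pre-dose fluid in a patient without a CR, for whom the other three places appear to retain it.

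Several parts of the protocol make this more than a matter of style:
- Section 2.8 justifies outpatient dosing partly by mandatory IV fluid around the alvocidib doses. It also describes a patient in an earlier monotherapy study, where TLS prophylaxis was not required, who had hyperacute TLS and needed dialysis.
- The Day 1 alvocidib dose rises from 25 mg/m² in Cycle 1 to 50 mg/m² from Cycle 2 (Section 4.4.2).
- Normal uric acid and phosphorus on entering Cycle 2 follow a cycle of mandatory hydration and allopurinol, so they say little about the patient's risk without them.
- The lab rule takes no account of remaining tumor burden, which is the subject of the caution in Section 4.5.1.1.

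**Working it through.** No figure in the plan needs reproducing. The check sets the rules against the patients who can reach Cycles 2+, then sizes the fluid at issue.

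**Step 1: who can enter Cycles 2+.** Section 5.3 admits patients with CR, CRi, CRh, MLFS, PR or clinical benefit. Patients without a CR are therefore expected.

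**Step 2: apply both rules.**

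| Patient at the start of a later cycle | Section 5.3.1 | Synopsis, 4.5.1.1, Appendix A (natural reading) | Agree? |
|---|---|---|---|
| CR, normal labs, no TLS | may stop | optional | yes |
| No CR, abnormal labs | stopping condition not met | continue | yes |
| No CR (e.g. PR), normal labs, no TLS | may stop | continue | **no** |
| CR, raised uric acid or phosphorus | stopping condition not met | optional | **no** |

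The rules disagree in both directions. The third row is the one that loses a safeguard.

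**Step 3: disease remaining in the third row.** Appendix E defines PR by a "decrease of bone marrow blast percentage to 5% to 25"%, with a fall of at least half from baseline. Clinical benefit has no blast limit. CRi, CRh and MLFS require marrow blasts below 5%, so they are of less concern.

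**Step 4: monitoring that remains.** TLS labs precede each dose in Cycles 2+. The labs 2 hours after post-dose hydration and on Days 2-4 belong to Cycle 1 (Section 4.5.1.1), although Section 2.8 says TLS usually shows within 72 hours, as seen with hybrid dosing. After Day 1 of a later cycle, the next scheduled labs in Arm 2 are at Day 8. Arm 1 has chemistry twice weekly during low-dose cytarabine (Section 5.3.3). Section 5.3.1 does not say which lab result governs: its decision falls at least 2 hours before dosing, while Section 5.3.2 collects Day 1 chemistry just before dosing.

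**Step 5: fluid at issue.** Inputs are 250-500 cc over 1-2 hours before alvocidib and the same after it (synopsis; Section 4.5.1.1), and alvocidib on Days 1 and 15 in Arm 1 or Days 1, 8 and 15 in Arm 2 (Section 4.4.2). The volumes are stated for Cycle 1, and using them for later cycles is an assumption.

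Pre-dose fluid per cycle = number of doses covered × volume per dose.
- Day 1 only, either arm (the section heading and restart instruction point to this): 1 × 250 to 1 × 500 = 250-500 cc.
- Every dose, Arm 1 (assumed reading): 2 × 250 to 2 × 500 = 0.5-1.0 L.
- Every dose, Arm 2 (assumed reading): 3 × 250 to 3 × 500 = 0.75-1.5 L.

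**The case against.** The strongest reply is that an explicit permission is being set against an inference. In the synopsis and Section 4.5.1.1, the mandate attaches to Cycle 1. No sentence says that patients without a CR must be hydrated later, and the word 'only' is absent. This is correct as a matter of wording. But an option confined to CR patients would serve little purpose if anyone with normal labs could stop, and Appendix A schedules hydration in Cycles 2+.

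SAP Section 18 also prints a phrase about TLS symptoms near the hydration row, which might support a symptom-driven rule. It cannot be placed in that row with certainty and may belong to the phosphate binder. It would not remove the Cycles 2+ hydration entries in any case.

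On risk, PR requires the blood counts of a CR and at least a halving of marrow blasts, and nothing in the protocol calls a PR marrow a high blast count. That stands, and it leaves clinical benefit as the clearer worry. There are real mitigations: labs before each dose, hydration checks at visits, fluid restarted if TLS is suspected, and the caution in Section 4.5.1.1. The allowance in Section 4.5 to adjust supportive-care doses does not say which stopping rule governs.

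Finally, aligning the other places to Section 5.3.1 would also remove the mismatch. It would, however, weaken the fluid prophylaxis on which Section 2.8 relies. The separate stopping rules in Section 4.5.1.1 also suggest that Section 5.3.1 is the drafting slip.

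**Conclusion.** The inconsistency holds. For a patient without a CR who has normal labs and no evidence of TLS, Section 5.3.1 permits omission of pre-dose fluid that the synopsis, Section 4.5.1.1 and Appendix A, naturally read, retain. The amount per affected patient is 250-500 cc per cycle on the Day 1 reading and up to 1.5 L per Arm 2 cycle if every dose is covered, both assuming Cycle 1 volumes.

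This is a safety-wording problem of moderate weight. Section 5.3.1 is permissive, so a site that keeps hydrating such patients complies with every section. The number of affected patients and any change in TLS risk cannot be derived from the documents, and no endpoint, sample size or analysis is touched. The SAP introduction records that the study closed on 17 November 2020 with 11 patients enrolled. The practical value now is clarity for anyone still on treatment and a correct text if the protocol is reused.

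**What to change.** Make two changes in Section 5.3.1.

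1. Remove IV hydration from the lab-based stopping sentence, leaving allopurinol and the phosphate binder. Add: *In Cycles 2+, pre- and post-infusion IV hydration follows Section 4.5.1.1: it is optional only for patients who have achieved a CR.*
2. Reword the next instruction so that suspected TLS is a reason to restart hydration where it was omitted, not the condition for giving it.

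The synopsis, Section 4.5.1.1 and Appendix A can stay as they are. The first change also resolves the reverse mismatch for CR patients with raised uric acid or phosphorus, and it places no new restriction on patients in CR.

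The cost is outpatient time. A non-CR patient with normal labs receives 250-500 cc over 1-2 hours before alvocidib that Section 5.3.1 would have let the site skip. If a site had stopped post-infusion fluid as well, the addition per dose is 2 × 250 to 2 × 500 = 500-1000 cc and 2 × 1 to 2 × 2 = 2-4 hours. This also applies to patients in CRi, CRh or MLFS, whose marrow blasts are below 5%.

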5.3.2 Cycles 2+: Day 1 Just Prior to First Dose

Perform the following procedures just prior to dosing on Day 1:

- Perform a complete physical examination including height (cm) and weight (kg) for calculation of body surface area (BSA) (Note: Dose is only adjusted at the beginning of each cycle after Cycle 1 if there has been a > 10% change in weight compared to the weight used to calculate the current dose.)
- Record vital signs measured prior to the initiation of infusion following a 5-minute rest
- Assess ECOG PS ([Appendix B](#))
- Collect blood for evaluation of laboratory parameters ([Appendix D](#)):
 - Hematology
 - Full serum chemistry panel
 - Coagulation: fibrinogen level as clinically indicated
- Collect urine or serum sample for β -hCG pregnancy test for females of child-bearing potential
- Record all concomitant medications, including all prescription drugs, nonprescription drugs, and nutritional supplements, administered in conjunction with an AE.
- Record all transfusions (PRBC and platelets) that have occurred while on study.
- Review study diary and remind patient to bring diary back at next clinic visit

5.3.3 Cycles 2+: Dosing Days: Arm 1: Days 1, 3–12, 15; Arm 2: Days 1, 8, 15

A ± 2 -day window will be allowed for Day 15 of both treatment arms. A ± 1 -day window will be allowed for Day 8 (Arm 2 only).

- Abbreviated physical examination (Arm 1: Day 15; Arm 2: Days 8 and 15)
- Assess ECOG PS (Arm 1: Day 15; Arm 2: Days 8 and 15) ([Appendix B](#))
- Record vital signs on Days 1, 8, and 15 in both arms

- Assess patients for adequate hydration at all study visits and replace excessive fluid losses, including from diarrhea, unless otherwise clinically indicated ([Section 4.5.1.2](#) and [Section 4.5.1.3](#))
- Collect blood for evaluation of laboratory parameters ([Appendix D](#)):
 - Hematology and full serum chemistry panel on each day of alvocidib administration (Arm 2) and twice weekly (minimum of 72 hours between collections) during LDAC treatment (ie, Days 3-12 of Arm 1)
 - Tumor lysis labs as indicated in [Section 4.5.1.1](#)
 - Coagulation: fibrinogen level as clinically indicated
- Record all concomitant medications, including all prescription drugs, nonprescription drugs, and nutritional supplements, administered in conjunction with an AE
- Administer prophylactic antibiotics and antivirals, and antifungals according to [Section 4.5.1.4](#)
- Assess for AEs
- Administer alvocidib or cytarabine according to [Section 4.4.2](#)
- Review study diary and remind patient to bring diary back at next clinic visit

Stage 2 dosing regimen will be selected based on results from Stage 1 arms in terms of response rates, relative safety, and risk-benefit ratio.

